5.5.9 Discontinuation of investigational treatment or premature study discontinuation

Patients may voluntarily discontinue the investigational treatment for any reason at any time.

The investigator should discontinue investigational treatment for a given patient if, on balance, he/she believes that continuation would be detrimental to the patient's well-being.

Investigational treatment *must* be discontinued under the following circumstances:

- Use of prohibited treatment as per [Table 5-1](#).
- Any other protocol deviation that results in a significant risk to the patient's safety
- Breaking of the blind (inadvertently or for emergency reasons)
- Severe hypersensitivity reaction occurs
- Liver event definition met as per [Appendix 2](#)
- Deviations from the prescribed dose regimen for investigational treatment with 2 doses missed at any time
- Death
- Withdrawal of consent
- Sponsor decision to terminate (part of) the study

Investigational treatment *may* be discontinued under the following circumstances:

- Emergence of the adverse events that in the judgment of the investigator, taking into account the patient's overall status, prevent the patient from continuing participation in the study
- Any laboratory abnormalities that in the judgment of the investigator, taking into consideration the patient's overall status, prevents the patient from continuing participation in the study

At the time of protocol amendment #2 implementation, patients who have already received their Week 20 infusion of investigational treatment returned to the site at their next scheduled

visit and performed their End of Treatment visit. They continued as per the study visit schedule Table 6.1.

Patients who discontinue investigational treatment are NOT considered immediately withdrawn from the STUDY or to have withdrawn informed consent to participation (described in section 5.5.10). The patient must return approximately 28 days following the patient's last investigational treatment administration to complete the End of Treatment visit assessments (Table 6-1). If the patient was already off-treatment for a longer period, then the End of Treatment visit can be performed without delay. After completing the End of Treatment assessments, patients will enter a 4-week follow up and return for the End of Study visit. If the patient fails to return for these assessments for unknown reasons, every effort should be made to contact him/her as specified in Section 5.5.11.

Investigators or site personnel must contact the IRT to register the patient's discontinuation from treatment. In addition, the investigator will report the primary reason for treatment discontinuation on the End of Treatment Epoch eCRF.

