7.3 Liver safety monitoring

To ensure patient safety and enhance reliability in determining the hepatotoxic potential of an investigational drug, a standardized process for identification, monitoring and evaluation of liver events will be followed.

The following two categories of abnormalities / adverse events have to be considered during the course of the study:

- Liver laboratory triggers, which will require repeated assessments of the abnormal laboratory parameter
- Liver events, which will require close observation, follow-up monitoring and completion of the standard liver CRF page

Please refer to [Table 14-1](#) in [Appendix 2](#) for complete definitions of liver laboratory triggers and liver events.

Every liver laboratory trigger or liver event as defined in [Table 14-1](#) of [Appendix 2](#) should be followed up by the investigator or designated personal at the trial site as summarized below. Detailed information is outlined in [Table 14-2](#) in [Appendix 2](#).

For the liver laboratory trigger:

- Repeating the LFT within the next week to confirm elevation.

These LFT repeats should be performed using the central laboratory if possible. If this is not possible, then the repeats can be performed at a local laboratory to monitor the safety of the patient. Repeat laboratory should then be performed at central laboratory as soon as possible. If a liver event is subsequently reported, any local LFTs previously conducted that are associated with this event should be reported on the Liver CRF pages.

- If the elevation is confirmed, close observation of the patient will be initiated, including consideration of treatment interruption if deemed appropriate.

For the liver events:

- Repeating the LFT to confirm elevation as appropriate
- Discontinuation of the investigational drug if appropriate
- Hospitalization of the patient if appropriate
- A causality assessment of the liver event via exclusion of alternative causes (e.g., disease, co-medications)
- An investigation of the liver event, which needs to be followed until resolution.

These investigations can include serology tests, imaging and pathology assessments, hepatologist's consultancy, based on investigator's discretion. All follow-up information, and the procedures performed should be recorded on appropriate eCRF pages, including the liver event overview eCRF pages.

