LIVER EVENTS	
 • $\text{ALT or AST} > 5 \times \text{ULN}$ • $\text{ALP} > 2 \times \text{ULN}$ (in the absence of known bone pathology) • $\text{TBL} > 2 \times \text{ULN}$ (in the absence of known Gilbert syndrome) • $\text{ALT or AST} > 3 \times \text{ULN}$ and $\text{INR} > 1.5$ • Potential Hy's Law cases (defined as $\text{ALT or AST} > 3 \times \text{ULN}$ and $\text{TBL} > 2 \times \text{ULN}$ [mainly conjugated fraction] without notable increase in ALP to $> 2 \times \text{ULN}$) • Any clinical event of jaundice (or equivalent term) • $\text{ALT or AST} > 3 \times \text{ULN}$ accompanied by (general) malaise, fatigue, abdominal pain, nausea, or vomiting, or rash with eosinophilia • Any adverse event potentially indicative of a liver toxicity *

*These events cover the following: hepatic failure, fibrosis and cirrhosis, and other liver damage-related conditions; the non-infectious hepatitis; the benign, malignant and unspecified liver neoplasms.

Table 14-2 Follow Up Requirements for Liver Events and Laboratory Triggers

Criteria	Actions required	Follow-up monitoring
Potential Hy's Law case ^a	
 • Discontinue the study drug immediately • Hospitalize, if clinically appropriate • Establish causality • Complete liver CRF 	ALT, AST, TBL, Alb, PT/INR, ALP and γ GT until resolution ^c (frequency at investigator discretion)
ALT or AST		
$> 8 \times \text{ULN}$	
 • Discontinue the study drug immediately • Repeat LFT within 48 hours • Hospitalize if clinically appropriate • Establish causality • Complete liver CRF 	ALT, AST, TBL, Alb, PT/INR, ALP and γ GT until resolution ^c (frequency at investigator discretion)
$> 3 \times \text{ULN}$ and $\text{INR} > 1.5$	
 • Discontinue the study drug immediately • Hospitalize, if clinically appropriate • Establish causality • Complete liver CRF 	ALT, AST, TBL, Alb, PT/INR, ALP and γ GT until resolution ^c (frequency at investigator discretion)
> 5 to $\leq 8 \times \text{ULN}$	
 • Repeat LFT within 48 hours • If elevation persists, continue follow-up monitoring • If elevation persists for more than 2 weeks, discontinue the study drug 	ALT, AST, TBL, Alb, PT/INR, ALP and γ GT until resolution ^c (frequency at investigator discretion)

Criteria	Actions required	Follow-up monitoring

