	
 Establish causality Complete liver CRF 	
> 3 × ULN accompanied by symptoms ^b	
 Discontinue the study drug immediately Hospitalize if clinically appropriate Establish causality Complete liver CRF 	ALT, AST, TBL, Alb, PT/INR, ALP and γGT until resolution ^c (frequency at investigator discretion)
> 3 to ≤ 5 × ULN (patient is asymptomatic)	
 Repeat LFT within the next week If elevation is confirmed, initiate close observation of the patient 	Investigator discretion Monitor LFT within 1 to 4 weeks
ALP (isolated)		
> 2 × ULN (in the absence of known bone pathology)	
 Repeat LFT within 48 hours If elevation persists, establish causality Complete liver CRF 	Investigator discretion Monitor LFT within 1 to 4 weeks or at next visit
TBL (isolated)		
> 2 × ULN (in the absence of known Gilbert syndrome)	
 Repeat LFT within 48 hours If elevation persists, discontinue the study drug immediately Hospitalize if clinically appropriate Establish causality Complete liver CRF 	ALT, AST, TBL, Alb, PT/INR, ALP and γGT until resolution ^c (frequency at investigator discretion) Test for hemolysis (e.g., reticulocytes, haptoglobin, unconjugated [indirect] bilirubin)
> 1.5 to ≤ 2 × ULN (patient is asymptomatic)	
 Repeat LFT within the next week If elevation is confirmed, initiate close observation of the patient 	Investigator discretion Monitor LFT within 1 to 4 weeks or at next visit
Jaundice	
 Discontinue the study drug immediately Hospitalize the patient Establish causality Complete liver CRF 	ALT, AST, TBL, Alb, PT/INR, ALP and γGT until resolution ^c (frequency at investigator discretion)
Any AE potentially indicative of a liver toxicity*	
 Consider study drug interruption or discontinuation Hospitalization if clinically appropriate Establish causality Complete liver CRF 	Investigator discretion

*These events cover the following: hepatic failure, fibrosis and cirrhosis, and other liver damage-related conditions; the non-infectious hepatitis; the benign, malignant and unspecified liver neoplasms

^aElevated ALT/AST > 3 × ULN and TBL > 2 × ULN but without notable increase in ALP to > 2 × ULN

^b(General) malaise, fatigue, abdominal pain, nausea, or vomiting, or rash with eosinophilia

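### Section 5.5.9 makes stopping mandatory for every Appendix 2 liver event, but Table 14-2 makes it conditional or discretionary for three of them

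*Protocol*

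**What the plan says.** Section 5.5.9 opens its first list with "Investigational treatment *must* be discontinued under the following circumstances", and one entry is "Liver event definition met as per" Appendix 2. The entry carries no condition on type, severity or persistence. A separate list follows of circumstances in which treatment *may* be stopped, including laboratory abnormalities left to the investigator's judgement. The glossary defines treatment discontinuation as a permanent stop.

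Appendix 2 holds two tables. Table 14-1 defines the liver events. Table 14-2 sets the action for each. For ALT/AST above 5 and up to 8 times ULN it asks for a repeat test, then "If elevation persists, continue follow-up monitoring", and stopping only when the elevation has lasted more than 2 weeks. For isolated bilirubin above 2 times ULN it stops drug only if a repeat within 48 hours confirms the elevation. For an adverse event suggesting liver toxicity it says "Consider study drug interruption or discontinuation".

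Section 7.3 summarises follow-up for liver events as a class, includes "Discontinuation of the investigational drug if appropriate", and sends the reader to Table 14-2 for detail.

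**The concern.** One section ties permanent discontinuation to a definition being met. The table written to manage those same events grades the response. Nothing in the protocol says which text prevails. Section 7.3 promises a standardised process, yet two sites acting in good faith could handle one laboratory result in opposite ways.

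The first thing at stake is consistent handling of a patient-safety rule. The second is data. Under 5.5.9 a patient who stops treatment leaves the normal visit schedule, with End of Treatment about 28 days after the last dose and End of Study four weeks later. The passage a site follows can therefore decide whether a Week 24 lean body mass scan exists.

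**Working it through.** The plan gives no figure to reproduce. The check sets the passages side by side and then works out visit days.

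**1. Each Table 14-1 liver event against its Table 14-2 action.** Section 5.5.9 read literally gives a permanent stop in every row.

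| Table 14-1 event | Table 14-2 action on study drug | Agrees with 5.5.9? |
|---|---|---|
| ALT/AST >5x ULN | >8x: stop at once; >5 to ≤8x: stop only if it persists more than 2 weeks | In part |
| ALP >2x ULN, no known bone pathology | None listed | Silent |
| TBL >2x ULN, no known Gilbert syndrome | Stop only if it persists on repeat | No |
| ALT/AST >3x ULN with INR >1.5 | Stop at once | Yes |
| Potential Hy's Law case | Stop at once | Yes |
| Jaundice | Stop at once | Yes |
| ALT/AST >3x ULN with symptoms | Stop at once | Yes |
| AE suggesting liver toxicity | Interruption or discontinuation to be considered | No |

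The count is 4 that agree, 3 that are conditional or discretionary (one of them in part) and 1 that is silent: 4 + 3 + 1 = 8.

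**2. When the two texts lead to different outcomes.** Doses are 28 days apart. A repeat within 48 hours, or a 14-day persistence check, will usually be settled before the next dose. If the elevation persists, both texts end in discontinuation, usually with the same last dose. If it resolves, 5.5.9 has already required a permanent stop and Table 14-2 requires none. For the adverse-event category the outcome depends on the site's judgement.

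**3. Consequence for the Week 24 scan.** Inputs:
- End of Treatment is about 28 days after the last dose (Protocol 5.5.9 and the footnote to Table 6-1).
- DXA is scheduled at Day 1, Week 12 and Week 24/End of Treatment only (Protocol Table 6-1).
- The DXA Week 12 window is Day 4 to 126, and the Week 24 window opens on Day 127 (SAP 3.5.1, DXA table).

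Formula: End of Treatment day ≈ day of last dose + 28.

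| Last dose | End of Treatment | DXA window |
|---|---|---|
| Week 4 | 28 + 28 = 56 | Week 12 |
| Week 8 | 56 + 28 = 84 | Week 12 |
| Week 12 | 84 + 28 = 112 | Week 12 |
| Week 16 | 112 + 28 = 140 | Week 24 |
| Week 20 | 140 + 28 = 168 | Week 24 |

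Visit windows do not change the Week 12 row. A Week 12 dose 4 days late and an End of Treatment visit 7 days late give 84 + 4 + 28 + 7 = 123, still before Day 127. The 7-day allowance is an assumption, borrowed from the Week 16–24 visit window.

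**4. Which results can trigger this.** Chemistry is scheduled at screening and Weeks 4, 8, 12, 24 and 48 (Protocol Table 6-3), and the last dose is at Week 20. On-treatment scheduled results that can still change dosing are therefore those at Weeks 4, 8 and 12. If drug is stopped before the next dose, all three leave the last dose at Week 12 or earlier. Later stops would come from unscheduled tests or clinical events.

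**The case against.** The strongest reply is that 5.5.9 cites Appendix 2 as a whole, whose title covers both definitions and follow-up requirements, so the reference could import the graded actions of Table 14-2. That reading is possible. It is the weaker one, because the trigger is the definition being met and the definitions are in Table 14-1. Two tenable readings of a stopping rule are themselves the problem.

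Four stronger claims that a reader might infer do not hold:
- *That no site can comply with all the passages.* A site that always stops breaches no row of Table 14-2. No row tells the site to keep dosing, and discontinuing is one of the options to be considered. The breach runs one way: a site that uses the latitude in Table 14-2 departs from 5.5.9.
- *That Section 7.3 is a third, independent rule.* It presents itself as a summary and defers to Table 14-2.
- *That isolated ALP is a conflict of equal weight.* Its row is silent on study drug. Its definition excludes known bone pathology, and every patient has a recent hip fracture. Whether a fracture counts is not stated.
- *That any liver stop loses the Week 24 outcome or puts the primary result at risk.* The scan is missed only when the last dose is at Week 12 or earlier, and that follows from the early End of Treatment rule, which is a separate design matter. The primary model assumes missing at random, and a placebo-based sensitivity analysis covers study discontinuation for adverse events. Nothing in the documents shows that the primary result would move.

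**Conclusion.** The inconsistency is in current protocol text and should be corrected. It is clearest for ALT/AST above 5 and up to 8 times ULN, where the 2-week condition has no purpose if stopping is already mandatory. It also holds for isolated bilirubin and for suggestive adverse events. Isolated ALP is a gap of uncertain relevance. The other four definitions, and ALT/AST above 8 times ULN, are consistent between 5.5.9 and Table 14-2.

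The practical difference is a permanent stop against continued dosing, mainly when an elevation resolves or when an adverse event is left to judgement. With the last dose at Week 12 or earlier, the stop also costs the scheduled Week 24 scan. This assumes that End of Treatment takes place about 28 days after the last dose; 5.5.9 lets it happen without delay for a patient already off drug for longer, so some could fall later. The documents give no expected rate of these events, and the number affected may be small. That limits the likely effect on the estimate, but a safety stopping rule still needs a single instruction.

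**What to change.** Reconcile Section 5.5.9 with Table 14-2 so that each Table 14-1 category, including isolated ALP, has one stated action on study drug. Have 5.5.9 refer to that single table, and align the summary in 7.3 with it. Which action is right for each category is a clinical decision for the sponsor and its safety advisers, and none is proposed here. The cost is protocol wording in the next amendment and a letter to investigators; the primary analysis model need not change.

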5.5.10 Withdrawal of consent

Patients may voluntarily withdraw consent to participate in the study for any reason at any time.

Withdrawal of consent occurs when a patient does not want to participate in the study any more, does not want any further visits or assessments, does not want any further study related contacts, and does not allow analysis of already obtained biologic material.

If a patient withdraws consent, the investigator must make every effort to determine the primary reason for this decision and record this information in the Withdrawal of Consent eCRF. Investigational treatment must be discontinued and no further assessments conducted. All biological material that has not been analyzed at the time of withdrawal must not be used. Further attempts to contact the patient are not allowed unless safety findings require communicating or follow-up.

5.5.11 Loss to follow up

For patients whose status is unclear because they fail to appear for study visits without stating an intention to withdraw, the investigator should show "due diligence" by contacting the patient, family or family physician as agreed in the informed consent and by documenting in the source documents steps taken to contact the patient, e.g. dates of telephone calls, registered letters, etc. A patient should not be considered lost to follow-up until his/her scheduled end of study visit would have occurred.

Subjects who are prematurely withdrawn from the study will not be replaced by an equal number of newly enrolled patients.

5.5.12 Emergency breaking of assigned treatment code

Emergency treatment code breaks should only be undertaken when it is essential to treat the patient safely and efficaciously. Most often, investigational treatment discontinuation and knowledge of the possible treatment assignment are sufficient to treat a study patient who presents with an emergency condition. Emergency treatment code breaks are performed using

the IRT. When the investigator contacts the system to break a treatment code for a patient, he/she must provide the requested patient identifying information and confirm the necessity to break the treatment code for the patient. The investigator will then receive details of the investigational drug treatment for the specified patient and a fax or email confirming this information. The system will automatically inform the Novartis monitor for the site and the Global Trial Leader (GTL) that the code has been broken.

It is the investigator's responsibility to ensure that there is a dependable, redundant procedure in place to allow access to the IRT/code break cards at any time in case of emergency. The investigator will provide protocol number, investigational treatment name if available, patient number as well as oral and written information to the subject on how to contact his/her backup in cases of emergency when he/she is unavailable to ensure that un-blinding can be performed at any time in the case of emergency.

Investigational treatment must be discontinued after emergency unblinding (Section 5.5.9).

5.5.13 Study completion and post-study treatment

A patient will be considered to have completed the study when he/she has completed 48 weeks of the study including the End of Study Visit.

The study will be considered to be complete when the last patient completes 48 weeks of the study including the End of Study Visit.

Patients who are still in the screening process once planned enrollment is met will be allowed to complete screening and will be randomized into the study if eligible.

[figure not shown]
The investigator must provide follow-up medical care for all patients who are prematurely withdrawn from the study, or must refer them for appropriate ongoing care.

5.5.14 Early study termination

The study can be terminated at any time for any reason by Novartis. Should this be necessary, the patient should be seen as soon as possible and treated as a patient prematurely withdrawn from the study. The investigator may be informed of additional procedures to be followed in order to ensure that adequate consideration is given to the protection of the patient's interests. The investigator will be responsible for informing the Institutional Review Board/Independent Ethics Committee (IRBs/IECs) of the early termination of the trial.

6 Visit schedule and assessments

Table 6-1 lists all of the assessments and indicates with an "x" when they are to be performed. Patients should be seen for all visits on the designated day within the recommended "visit window" specified below, or as close to it as possible. The site should make every effort to help bring the patients to the clinic visits, including providing transportation if necessary. If any visits are delayed or missed, the site personnel should ensure alignment of future patient visits according to the originally planned visit schedule (i.e. rescheduled visit window needs to be calculated with reference to first dose received; day of randomization and first dose received may differ occasionally), and should ensure that 2 consecutive infusions are done at least 14 days apart.

Recommended visit windows:

Randomization/Day 1: + 2 days

Weeks 4-12: +/- 4 days

Weeks 16-24: +/- 7 days

Weeks 36-48: +/- 14 days

Some of the following principles should be taken into consideration when scheduling a visit:

- Assessments for a particular visit - including the randomization visit - may be split over several days.
- [REDACTED] physical performance tests should be considered early in the visit to avoid physical or mental exhaustion of the patient.
- Laboratory work in particular those requiring 8 hours fasting should be done early in order to allow the patients to eat and drink
- Patient dosing should be the last procedure to be performed

During the treatment epoch, patients may be seen at unscheduled visits for instance for AEs that in the opinion of the investigator need intervention or repeated laboratory testing. All relevant safety assessments may be performed as deemed necessary by the investigator. During these unscheduled visits, investigational treatment must **NOT** be administered.

During the post-treatment follow up epoch, safety and efficacy assessments will continue until the EoS visit at week 48. .

[figure not shown]
[figure not shown]
[figure not shown]
[figure not shown]

Table 6-1 Assessment schedule

Study Epoch	Screening	Treatment							Post-treatment follow up		Notes
Visit name/study week	Screening / Day -39 to -1	BL/ Rand Day 1	Week 4	Week 8	Week 12	Week 16	Week 20	End of treatment / Week 24 *	Week 36	End of study / Week 48	
Days post-op or post 1st dose	D3 to 42 post- op	1	28	56	84	112	140	168	252	336	
Informed Consent	X										
Verify Inclusion/ Exclusion	X										
Randomization		X									
Demographics	X										
MMSE	S										Source documents only.
Hip fracture history	X										
Medical history	X										
Physical Examination	S				S			S		S	Source documents only.
Blood sample for serology	X										
Blood sample for hematology and chemistry	X		X	X	X			X		X	
Blood sample for hormones	X				X			X		X	
Urine sample	X		X	X	X			X		X	
Vital Signs	X	X	X	X	X	X	X	X	X	X	
Height	X										
Weight	X	X	X	X	X	X	X	X	X	X	
12-lead ECG (triplicate)	X	X			X			X			
Echocardiography								(X)		(X)	Only for patients enrolled

Study Epoch	Screening	Treatment							Post-treatment follow up		Notes
Visit name/study week	Screening / Day -39 to -1	BL/ Rand Day 1	Week 4	Week 8	Week 12	Week 16	Week 20	End of treatment / Week 24 *	Week 36	End of study / Week 48	
Days post-op or post 1 st dose	D3 to 42 post- op	1	28	56	84	112	140	168	252	336	
											before Amendment #3. W48 is to be performed only if W24 reading indicates clinically meaningful abnormality as per central reader's assessment.
Gait Speed	S										Source document only.
SPPB (incl. gait speed)		X	X	X	X	X	X	X	X	X	
DXA		X			X			X			All centrally read.
X-ray	X							X	(X)	(X)	At screening local X-ray taken during or after surgery is to be used. If bone union is incomplete at W24 per central reading, X-rays need to be performed until this is achieved at W36 and potentially W48 as well.
Drug administration		X	X	X	X	X	X				

Study Epoch	Screening	Treatment							Post-treatment follow up		Notes
Visit name/study week	Screening / Day -39 to -1	BL/ Rand Day 1	Week 4	Week 8	Week 12	Week 16	Week 20	End of treatment / Week 24 *	Week 36	End of study / Week 48	
Days post-op or post 1 st dose	D3 to 42 post- op	1	28	56	84	112	140	168	252	336	
AE/SAE reporting	To be recorded as needed										
Medications and medical procedures	To be recorded as needed										

* In case of investigational treatment discontinuation during the Treatment Epoch, the patient should complete the EoT Visit 4 weeks after the last investigational treatment administration. After the EoT visit is completed, the patient should return after an additional 4 weeks for an EoS visit. In case of premature study discontinuation after the Treatment Epoch, the patient should return to an EoS visit (not earlier than 4 weeks after the EoT visit)
 
Rand = randomization; BL = baseline; Folstein Mini Mental State Examination =MMSE
											

